6.1. Primary Safety Endpoints

The primary safety endpoint of the study is the incidence of obscuration of the bones of the hand at 1, 6, 12 and 24 months. The primary safety variable is number and percent of subjects with an X-ray of either hand with obscuration of the bones of the hand at 1-, 6-, 12-, and 24-months as interpreted by at least 1 of 2 blinded radiologists at the imaging core lab.

The primary event of interest is whether treatment with Radiesse® interferes with radiological assessment by obscuring the bones of the hand at any time during the study. This will be based on assessments performed post-treatment. Analysis will be made by subject, and reported. In addition, for subjects with pre-treatment assessments, paired comparisons will be made informally to assess clinically relevant issues on the pre/post treatment X-rays. Corresponding two-by-two tables for paired measurements, and 95% exact binomial confidence intervals for results by visit will be calculated. Formal hypothesis tests are not planned but nominal results from tests may be reported based on exploratory analyses and subsequently interpreted as such.

6.2. Secondary Safety Endpoints

- The rate of device/injection-related severe AEs at 1- and 6-months

AEs will be summarized descriptively using MedDRA classification version X.X including duration, severity, relationship to study device, incidence of recurrence, and need for treatment by hand. The analysis will include the incidence of all AEs at 1- and 6- months.

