6 INVESTIGATIONAL PLAN

6.1 Overall study design

This is a prospective, open-label 2 year PAS evaluating radiographic appearance of Radiesse implantation in the dorsum of the hands in 20 subjects (40 hands). All subjects will be new subjects who did not participate in the pre-market Radiesse hand treatment study (Merz #P110607). Subjects will be consented at 1 investigational site in the United States.

Multiple assessments will be performed at study visits. Some of the main assessments include:

- X-rays – X-rays will be taken at a licensed radiographic imaging center and transmitted to the imaging core lab to be assessed by two blinded, licensed radiologists
- MHGS (**Figure 1**) – a single blinded site evaluator will grade the hands using the MHGS

- MHQ – subjects will self-report assessment of the effect(s) of Radiesse injection on hand function using the MHQ
- GAIS (**Table 1**) – subjects will rate the aesthetically pleasing aspect of the Radiesse hand treatment using the GAIS
- AE Subject Diary – subjects use this to collect any AEs for 30 days post injection
- Photographs – at baseline and exit from the study, and during the study to document a serious or medically concerning adverse event in the hands.

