Month 6: 180 ± 10 days from enrollment, all subjects will return for a follow-up visit. Changes in concomitant medications will be recorded by the study staff. The subject's hands will be assessed on the MHGS by a live, masked evaluator. Subject self-assessment of aesthetic improvement will be performed using the GAIS. Subjects will complete the MHQ.

A physician will assess the subject's hands for AEs. A urine pregnancy test will be completed for female subjects of child bearing potential. A Radiesse retreatment will be performed on both hands if agreed upon by treating investigator and subject. A take-home 30-day diary will be given to the subject if a retreatment is received. Photographs of the hands will be taken only in the event of a serious or medically concerning AE.

72 hours after Month 6 retreatment: Only subjects receiving a retreatment at the Month 6 visit will be scheduled for a phone visit 72 hours after treatment to assess for adverse events. Subjects will be reminded to continue daily entries into their 30-day diary.

Month 7: $210 \text{ days} \pm 5$ days from enrollment, only subjects who received a retreatment at Month 6 will return for a follow-up visit. Changes in concomitant medications will be recorded by the study staff. The subject's hands will be assessed on the MHGS by a live, masked evaluator. Subject self-assessment of aesthetic improvement will be performed using the GAIS. Subjects will complete the MHQ.

A physician will assess the subject's hands for AEs. The take-home 30-day diary will be reviewed for completion and collected. Photographs of the hands will be taken only in the event of a serious or medically concerning AE.

Month 12 X-rays: 360 ± 10 days from enrollment, only subjects whose hand bones were not visible in the Month 6 X-rays will have X-rays taken of their hands at a designated, local, licensed imaging center. This visit must be completed prior to the Month 12 follow-up visit at the investigational site.

Month 12: 360 ± 10 days from enrollment, all subjects will return for a follow-up visit. Changes in concomitant medications will be recorded by the study staff. The subject's hands will be assessed on the MHGS by a live, masked evaluator. Subject self-assessment of aesthetic improvement will be performed using the GAIS. Subjects will complete the MHQ.

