12.3.3 Other efficacy and safety variables

Other efficacy and safety variables are as follows:

- MHGS at 12-, 18-, and 24-months after initial treatment
- MHGS at 12- and 18-months follow retreatment for those receiving retreatment
- GAIS at 12-, 18-, and 24-months after initial treatment
- GAIS at 12- and 18-months follow retreatment for those receiving retreatment
- The rate of device/injection-related severe adverse events at 12-, 18- and 24-months
- Incidence of all AEs over the course of the study

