12.4.2 Secondary and other efficacy and safety variables

Analysis will be performed to determine MHGS changes from baseline, and if treatment effects were aesthetically pleasing in the hands after treatment as reported on the GAIS Threshold of MHGS improvement will be at least 1 point improved for effective analysis, as percent of subjects with both hands improved. Groups A and B will be analyzed separately and in aggregate. Confidence intervals will be based on a 5% nominal alpha level.

AEs will be summarized descriptively including type, duration, severity, relationship to study device, incidence of recurrence, and need for treatment by hand. The analysis will include the incidence of all AEs over the course of the study.

Descriptive statistics will be provided for the MHQ at baseline, study exit, and other collected time points. [REDACTED]

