6.3. Other Safety Endpoints

- Incidence of all AEs over the course of the study

AEs will be summarized descriptively including type, duration, severity, relationship to study device, incidence of recurrence, and need for treatment by hand. The analysis will include the incidence of all AEs over the course of the study.

[figure not shown]

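### Whole-study and later AE rates pool subjects with one to four injections, so they mix exposure, collection intensity and risk and do not address the objective on safety of multiple retreatments

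*SAP*

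**What the plan says.** **Planned AE results.** SAP 6.2 lists "The rate of device/injection-related severe AEs at 1- and 6-months" and adds: "The analysis will include the incidence of all AEs at 1- and 6- months". SAP 6.3 states: "The analysis will include the incidence of all AEs over the course of the study". Protocol 12.3.3 lists "The rate of device/injection-related severe adverse events at 12-, 18- and 24-months". Both documents analyse all enrolled subjects with available data (protocol 12.2, SAP 4).

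**How AEs are collected.** Protocol 6.1 describes the diary: "AE Subject Diary – subjects use this to collect any AEs for 30 days post injection". Protocol 6.1.1 and 9.2 add a 72-hour call and a 1-month visit after each injection. For Month 7, "only subjects who received a retreatment at Month 6 will return for a follow-up visit"; Months 13 and 19 work the same way. Outside those windows, scheduled collection is a physician assessment at Months 6, 12, 18 and 24. Protocol 10 records all AEs from consent to the last visit, with start and stop dates, and 9.2 allows unscheduled visits.

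**Retreatment.** Each subject may have none to three retreatments, by agreement with the treating investigator. Protocol 5.1 and SAP 5 name the safety of multiple retreatments as an objective. SAP 6.4 defines MHGS and GAIS results at 1 and 6 months following retreatment.

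**What the readable text lacks.** SAP 6.2 and 6.3 do not tie AEs to an injection, give no denominator by injection or subject-time, do not split by number of treatments, and do not say whether a rate at a given month is interval or cumulative. Parts of SAP section 6 are redacted or not shown, so this describes only what can be read.

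**The concern.** A subject treated four times has more real exposure than a subject treated once, and is also watched more closely. Whole-study incidence over all enrolled subjects therefore depends on how many retreatments subjects happened to choose. The same product with the same risk per injection would give a different headline figure under a different uptake of retreatment.

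The objective asks whether repeated treatment is safe. That needs AE results for the first, second, third and fourth injections, or at least by number received. The efficacy scales can be read that way under SAP 6.4; the AE results, as written, cannot.

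A smaller gap concerns the 6-month figure. The first retreatment is given at the Month 6 visit, and the SAP does not say that the figure stops at the AE assessment before it.

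**Working it through.** **1. Reproduce the stated visit counts.** From protocol 9.2, office visits are Screening, Week 1 and Months 1, 6, 12, 18, 24 = 7; adding Months 7, 13, 19 gives 10. X-ray visits are 3 to 5 and calls 1 to 4. The maximum is 10 + 5 = 15 visits and 4 calls. This agrees with protocol 6.1.1.

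**2. AE collection by number of retreatments k.** Calls = 1 + k. Physician AE visits after the first injection = 5 + k (Months 1, 6, 12, 18, 24, plus one per retreatment). Nominal diary days = 30(1 + k). Follow-up from a nominal Day 7 injection to Day 720 is 713 days.

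| Retreatments k | Calls + visits | Diary days | Diary share of 713 days | Days outside diary windows |
|---|---|---|---|---|
| 0 | 1 + 5 = 6 | 30 | 4.2% | 683 |
| 1 | 2 + 6 = 8 | 60 | 8.4% | 653 |
| 2 | 3 + 7 = 10 | 90 | 12.6% | 623 |
| 3 | 4 + 8 = 12 | 120 | 16.8% | 593 |

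Contacts rise by a factor of 1.33 to 2, and diary days by a factor of 2 to 4.

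**3. Effect of exposure alone (assumed risk).** The documents give no AE rate. If each injection carries the same independent risk p, the chance of at least one AE is 1 − (1 − p)^(k+1).

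| p per injection | 1 injection | 2 | 3 | 4 |
|---|---|---|---|---|
| 5% | 5.0% | 9.8% | 14.3% | 18.5% |
| 10% | 10.0% | 19.0% | 27.1% | 34.4% |
| 20% | 20.0% | 36.0% | 48.8% | 59.0% |

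A per-injection tabulation would show p in every column.

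**4. Effect of collection alone (assumed capture).** Take a constant true rate, 95% capture on diary days and 30% to 80% on other days. Captured events for four injections relative to one:
- 30% off diary: (0.95 × 120 + 0.30 × 593) / (0.95 × 30 + 0.30 × 683) = 291.9 / 233.4 = 1.25
- 80% off diary: (114 + 474.4) / (28.5 + 546.4) = 588.4 / 574.9 = 1.02

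On these assumptions the detection effect is much smaller than the exposure effect in step 3.

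**5. Are the windows after each injection equal?** The Month 1 visit is 25 to 35 days after the initial injection. Month 6 is Day 170 to 190 and Month 7 is Day 205 to 215, both counted from enrollment. The 1-month visit after that retreatment can therefore fall 205 − 190 = 15 to 215 − 170 = 45 days after it. The windows are only nominally equal.

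**The case against.** Four stronger readings are tempting and are not supported.

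- *Groups A and B differ in AE detection by design.* They do not. Both have one schedule and one retreatment rule, and any later divergence would need unequal uptake, for which no figure is given. Nor is an AE comparison by group clearly planned. The sentence "Groups A and B will be analyzed separately and in aggregate" in protocol 12.4.2 sits in the MHGS and GAIS paragraph, the SAP repeats it under efficacy (6.4), and SAP 10 stratifies only the primary endpoints. The 12.4.2 heading does cover safety variables, so some ambiguity remains.
- *Retreatment distorts the 1- and 6-month rates.* Up to the Month 6 assessment every subject has one injection, one diary, one call and the same two visits. Only the missing cut before retreatment is open.
- *AE rates will appear to fall after Month 1.* This needs interval rates, which the SAP does not specify, and a capture rate that no document gives. A cumulative incidence cannot fall.
- *Outside the diary window there is only recall.* Physicians assess the hands at each six-monthly visit, and subjects can prompt an unscheduled visit.

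Three further points stand. The rates at 12, 18 and 24 months cover severe events only, defined as incapacitating, which probably depend less on a diary. More injections carry more real risk, so a higher incidence in retreated subjects is not merely a detection artefact. And with 20 subjects and descriptive summaries, more splits mean very small counts. None of these lets a pooled incidence answer the retreatment question.

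**Conclusion.** The point holds for whole-study AE incidence (SAP 6.3) and, with less force, for the later severe-AE rates (protocol 12.3.3). These figures combine one to four injections per subject, 30 to 120 nominal diary days and 6 to 12 scheduled AE contacts. They cannot show whether repeated treatment is as safe as the first.

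The counts come from the documents. The size of the effect on incidence rests on assumptions: 10% to 34% across one to four injections at a 10% risk per injection, and a factor of 1.02 to 1.25 from collection intensity alone. The mix of retreatments is unknown, so the net effect on the reported figure cannot be stated. This is a gap in the AE tabulations. It is not evidence that the groups or the 1- and 6-month rates are biased.

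**What to change.** In SAP 6.2 and 6.3:

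1. Tabulate AEs with onset within 30 days of each injection, by treatment number (initial, first, second, third retreatment), with all injections given as the denominator. An event reported by call or visit counts even if no diary came back. Treat one session as one injection and keep the by-hand summaries already planned.
2. Tabulate AEs with onset outside those windows per subject-month.
3. Report whole-study incidence by number of treatments received, beside the overall figure.
4. Define each by-month rate as interval or cumulative, and cut the 6-month figure at the AE assessment before the Month 6 retreatment.
5. If AEs are compared between Groups A and B, use the period from the initial injection to that assessment, when both groups have the same schedule.

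This needs SAP wording and a few table splits from start dates already recorded; no new data are collected. Cells will be small: with 10 subjects and no events, the exact 95% upper limit is 30.8%. The 15 to 45 day spread of the post-retreatment visit should be stated in a table note. Because retreatment is a choice made during the study, items 1 and 3 should be read descriptively: subjects who return for more injections may be those who tolerated earlier ones.

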6.3. Other Safety Endpoints

- Incidence of all AEs over the course of the study

AEs will be summarized descriptively including type, duration, severity, relationship to study device, incidence of recurrence, and need for treatment by hand. The analysis will include the incidence of all AEs over the course of the study.

[figure not shown]
6.4. Secondary Efficacy Endpoints

The secondary efficacy variables are as follows:

- The number and percent of subjects with at least a 1 point improvement in MHGS in both hands at 1- and 6-months after initial treatment
- The number and percent of subjects with at least a 1 point improvement in MHGS in both hands at MHGS at 1- and 6-months following retreatment for those receiving retreatment
- The frequency distribution of GAIS values at 1 and 6-months after initial treatment
- The frequency distribution of GAIS values at 1- and 6-months following retreatment for those receiving retreatment
- MHQ scores at baseline, study exit, and other collected time points

Analysis will be performed to determine MHGS changes from baseline, and if treatment effects were aesthetically pleasing in the hands after treatment as reported on the GAIS. Threshold of MHGS improvement will be at least 1 point improved for effective analysis, as a percent of subjects with both hands improved. Groups A and B will be analyzed separately and in aggregate. Ninety-five percent confidence intervals will be constructed about the estimate of the proportion of subjects with improvement in both hands. Missing MHGS data will be imputed as no change.

Descriptive statistics will be provided for the MHQ at baseline, study exit, and other collected time points. The MHQ scores used for this summary will be calculated within the database or by statistical programming at the time of analysis. The MHQ scores entered by the site will not be used for this analysis.

- [REDACTED]
[REDACTED]
- [REDACTED]
[REDACTED]
[REDACTED]
[REDACTED]
[REDACTED]
- [REDACTED]
[REDACTED]
[REDACTED]

7. Study Subjects

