5 STUDY OBJECTIVES AND ENDPOINTS

5.1 Objectives

The primary objective of the study is to provide a preliminary assessment of the radiographic appearance of Radiesse material that has been injected into the dorsum of the hands. The assessment will be with X-rays, as interpreted by a remote imaging core lab. Based on preliminary radiographic data of Radiesse implantation in the face³, it is expected that Radiesse injection(s) in the hands will not obscure the bones as seen on plain X-rays of the hand; however, this is not being evaluated with hypothesis testing.

Other objectives of the study include evaluating the effectiveness of Radiesse implantation for very severe volume loss in the dorsum of the hands, the rate of device/injection-related severe adverse events, the safety of multiple retreatments with Radiesse in the dorsum of the hands.

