7.2 Inclusion criteria

Only subjects meeting all of the following inclusion criteria will be considered for study enrollment:

1. Has hands rating 2, 3, or 4 on the validated MHGS as determined by a live, masked evaluator.
 - Left and/or right hand with a rating of 4 of the validated MHGS will be assigned to Group A.
 - Left and right hands with a rating of 2 or 3 on the validated MHGS will be assigned to Group B.
3. Is at least 22 years of age.⁵
4. Has signed an ICF.
5. Understands and accepts the obligation not to receive any other procedures in the dorsum of the hands through the end of the study.

⁵ Pediatric populations or subpopulations generally do not suffer from the hand condition the device is intended to treat in the study protocol.

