9 STUDY ASSESSMENTS

9.1 Clinical evaluations

9.1.1 *Training and masking of MHGS evaluators*

The MHGS (**Figure 1**) will be used to measure clinical effectiveness of the Radiesse hand treatments by a masked evaluator performing live dorsal hand assessments. The MHGS is an ordinal scale and therefore ratings will be made based on a “snap-shot” at a time point and will not be based on a comparison to a pre-treatment photograph. The evaluator will remain masked throughout the study and blinded to knowledge of 0 to 3 repeat treatments during the study. Prior to study initiation, the masked evaluator will be trained and qualified by the study Sponsor to perform MHGS assessments. Training will consist of an instructional webinar and qualification will consist of the masked evaluator trainee scoring 2 25-subject photo booklets, at least 1 week apart for intra-rater weighted Kappa analyses prior to study initiation. Retraining will occur if a minimal weighted Kappa value is not achieved (≥ 0.60), with qualification required prior to screening subjects for the study, prior to initial X-ray and Radiesse treatment in the study. If a repeat hand treatment is scheduled during a study visit, the MHGS assessment will be completed prior to treatment. To ensure that the blind is maintained, subjects will have their upper body and face hidden behind a barrier screen with only their hand visible to the masked evaluator. Subjects will be asked to remain silent during the MHGS evaluation process. Masked evaluators will not be allowed to discuss treatment schedules with treatment investigators and study staff at the site, and will not enter data on case report forms (CRFs) that contain information that would break the blind.

9.1.2 *Evaluation of aesthetic improvement*

To assess the aesthetically pleasing aspect of the Radiesse hand treatment outcomes, subjects will perform self-assessments on the GAIS shown in **Table 1**. The GAIS is a relative scale, therefore the subjects will be asked to perform the rating compared to baseline pre-treatment photographs.

9.1.3 *Evaluation of hand function*

Subjective functional outcomes will also be assessed at baseline and at 1-, 3-, 6-, 7-, 12-, 13-, 18-, 19- and 24-months following initial injection of Radiesse using the validated MHQ (**Appendix C**). The MHQ is a patient-rated outcome tool based on psychometric principles that is capable of measuring health status domains that are important to patients with hand disorders.

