Week 1/Initial treatment visit: 7 ± 6 days from enrollment, all subjects will return for a follow-up visit after completing the corresponding X-ray visit to the designated imaging center. This visit can be scheduled on the same day as the X-ray visit. Females of childbearing age will complete a urine pregnancy test. The subject's hands will be assessed on the MHGS by a live, masked evaluator. Subjects will complete the MHQ [REDACTED] [REDACTED]. At this time, subjects will receive a Radiesse treatment. A take-home 30-day diary will be given to the subject. A physician will assess the subject's hands for AEs. Photographs of the hands will be taken only in the event of a serious or medically concerning AE. Subjects will be scheduled for the Month 1 X-ray and follow-up visits.

Follow-Up Evaluations

72 hours after Week 1/initial treatment: Subjects will be scheduled for a phone visit 72 hours after treatment to assess for AEs. Subjects will be reminded to continue daily entries into their 30-day diary.

Month 1 X-rays: 30 ± 5 days from enrollment, all subjects will have x-rays taken of their hands at a designated, local, licensed imaging center. This visit must be completed prior to the Month 1 follow-up visit at the investigational site.

Month 1: 30 ± 5 days from initial treatment, all subjects will return for a follow-up visit after completing the corresponding X-ray visit to the designated imaging center. Changes in concomitant medications will be recorded by the study staff. The subject's hands will be assessed on the MHGS by a live, masked evaluator. Subject self-assessment of aesthetic improvement will be performed using the GAIS. Subjects will complete the MHQ [REDACTED].

[REDACTED] A physician will assess the subject's hands for AEs. The take-home 30-day diary will be reviewed for completion and

collected. A physician will assess the subject's hands for AEs. Photographs of the hands will be taken only in the event of a serious or medically concerning AE.

Month 6 X-rays: 180 ± 10 days from enrollment, all subjects will have X-rays taken of their hands at a designated, local, licensed imaging center. This visit must be completed prior to the Month 6 follow-up visit at the investigational site.

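### The Group A response rate on the MHGS includes an unmeasured share of noise responders, because entry uses one top-grade rating, response is a single 1-grade fall, and the baseline is undefined

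*SAP*

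**What the plan says.** Protocol 5.1 lists among its objectives "evaluating the effectiveness of Radiesse implantation for very severe volume loss in the dorsum of the hands". The measure that serves it in SAP 6.4 is the count and percentage of subjects whose two hands both improve by one grade or more, taken separately one month and six months after the first injection. The threshold is one grade, with both hands required: "Threshold of MHGS improvement will be at least 1 point improved for effective analysis, as a percent of subjects with both hands improved". Results are given for each group and for both together, with 95% confidence intervals, and missing MHGS values count as no change.

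On entry, Protocol 7.2 says "Left and/or right hand with a rating of 4 of the validated MHGS will be assigned to Group A". Grade 4 is the highest eligible grade. The deciding rating is the one made by the masked evaluator at screening (Protocol 9.2).

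On measurement, Protocol 6.1 says "a single blinded site evaluator will grade the hands using the MHGS". Under Protocol 9.1.1 that evaluator qualifies on photo booklets at an intra-rater weighted kappa of 0.60 or more. The type of weights is not given.

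On baseline, SAP 6.4 speaks of changes from baseline without naming the rating. The Week 1 visit text in Protocol 9.2, describing the period before injection, states that the subject's "hands will be assessed on the MHGS by a live, masked evaluator". Table 2, as it reads in the copy reviewed, marks no MHGS at Week 1.

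**The concern.** A group chosen because one noisy rating sat at the top of the eligible range will, on average, rate lower next time even if nothing has changed. If screening is the baseline, a grade-4 hand counts as improved on any later rating of 3 or below. That is the smallest step on the scale, and it needs no second rating to support it. All subjects are treated and there is no comparison arm, so the trial has no planned estimate of how often this happens by itself.

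At stake is how the Group A percentage is read. With 10 subjects per group, each responder moves it by 10 points. A reader who sees the percentage and its interval cannot tell how much of it would appear with no effect.

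**Working it through.** The documents give no expected response rate, benchmark or noise rate, so there is no planned figure to reproduce. The check is a simulation under zero treatment effect.

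**Inputs from the documents**
- Response: at least 1 grade better in both hands at one visit (SAP 6.4).
- Group A: grade 4 in one or both hands; eligible grades 2 to 4 (Protocol 7.2).
- Weighted kappa floor 0.60 (Protocol 9.1.1).
- 10 subjects per group (Protocol 7).

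**Assumptions (not in the documents)**
- Five grades, 0 to 4 (the scale figure is not shown).
- True severity of a hand = subject mean (normal, mean 2.5, SD 1.0) + hand term (normal, SD 0.3).
- Rating = true severity + normal error, rounded and limited to 0-4.
- Error SD set so that two readings of a photo set spread evenly over the scale give the chosen linear weighted kappa: 0.74 for kappa 0.60, 0.54 for 0.70, 0.35 for 0.80.
- Correlation of the two hands' errors within a visit: 0 or 0.5.
- In Group A, the hand that is not grade 4 is at least grade 2.

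**Quantity computed:** P(both hands rated at least 1 grade below baseline at one later visit | group entry), with true severity unchanged. Ranges run from error correlation 0 to 0.5.

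| Linear kappa | Baseline | Group A, actual entry rule | Group B |
|---|---|---|---|
| 0.60 | Screening | 12.5-22% | 10.7-16.4% |
| 0.60 | Week 1 | 7-12% | 10-16% |
| 0.70 | Screening | 8.5-15.6% | 7.5-12.3% |
| 0.80 | Screening | 4.3-8.4% | 3.9-7.0% |

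For subjects with both hands at grade 4, the first row becomes 14-24%. Under the model they are only 36% (correlation 0) to 47% (correlation 0.5) of Group A.

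**In subjects**, at kappa 0.60 with screening as baseline:
- Expected noise responders among 10: 10 × 0.125 = 1.25 to 10 × 0.22 = 2.2.
- Chance of at least one: 1 − 0.875^10 = 74% to 1 − 0.78^10 = 92%.

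**Sensitivity to the assumptions.** Raising the assumed mean severity from 2.5 to 3.0 gives 9.5-16.8% for Group A. A second latent-normal model used four grade mixes, both kappa weightings, and entry on either or both hands, at kappa 0.60 with screening as baseline:

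| Between-hand error correlation | Linear weights | Quadratic weights |
|---|---|---|
| 0 | 5-11% | 9-22% |
| 0.5 | 10-18% | 17-34% |
| 0.8 | 15-28% | 23-44% |

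This gives the overall span of roughly 5-44%. It leaves out the extreme in which the two hands share all their error.

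**Scoring against both pre-injection ratings.** Requiring at least 1 grade better than both screening and Week 1 lowers the zero-effect rate at linear kappa 0.60 from 14-24% to 4-9% in subjects with both hands at grade 4.

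**The case against.** The strongest reply is that the size is not in the documents. The kappa weights, the grade mix, the scale range and the between-hand error correlation are all assumed. The value 0.60 is a floor and is measured on photographs, so a better rater makes the problem small. The plan already requires both hands to improve, masks the evaluator, counts missing values as no change and reports Months 1 and 6 separately. The endpoint is secondary, with no success criterion or planned test. All of this stands. It limits the point to interpretation and requires a range rather than one figure. It does not remove the mechanism: the simulated rates already include the both-hands rule, and repeatability on live hands is not measured.

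Four stronger readings are tempting, and the documents do not support them.

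- **That 14-24% of Group A would be false responders.** This applies only to subjects with both hands at grade 4. Protocol 7.2 admits subjects with one such hand.
- **That noise makes Group A look better than Group B.** With Week 1 as baseline the order reverses (7-12% against 10-16%), and no comparison of the groups is planned.
- **That the zero-effect rate is a share of the observed rate, or can be subtracted from it.** A noise responder must be someone who would not otherwise respond. As an illustration, with 80% true responders, a 12.5-22% rate adds at most 0.20 × 12.5 = 2.5 to 0.20 × 22 = 4.4 points. Error also turns some true responders into non-responders. An estimate from 10 subjects is too imprecise to subtract, and it spans only 1 to 13 days.
- **That effectiveness should require response at both Month 1 and Month 6.** That would measure durability. In simulation with a true 1.5-grade effect at kappa 0.60, combining it with the two-baseline rule cut the Group A rate from about 69-76% to 38-45%.

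**Conclusion.** The concern holds as a gap in interpretation. If screening is the baseline, some Group A subjects will meet the effectiveness rule through rating error and regression to the mean alone, and the plan neither measures nor bounds this. The best single statement is 12-22% at linear kappa 0.60, under the listed severity model and an error correlation of 0 to 0.5. Other plausible assumptions at that kappa give roughly 5-44%, and kappa 0.80 gives about 4-8% under the first model. Using Week 1 as the baseline reduces the rate to 7-12% at kappa 0.60 without removing it, so the undefined baseline matters as much as the threshold. No formal test is affected. The change is worth making because it is cheap and because effectiveness in very severe volume loss is a stated objective.

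**What to change.** In SAP 6.4 and Protocol 12.3.2 and 12.4.2:

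- **(a)** Report, by group and pooled, with exact 95% confidence intervals, the percent of subjects who meet the 1-point both-hands rule between screening and Week 1, before any injection. Present it as context for the response rate, not as a figure to subtract.
- **(b)** Beside the planned Month 1 and Month 6 rates, report a sensitivity rate that requires each hand to be at least 1 grade better than both pre-injection ratings.
- **(c)** State which pre-injection rating is the MHGS baseline. Reconcile the Week 1 visit text in Protocol 9.2 with Table 2, because (a) and (b) depend on that rating being taken.

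The cost is SAP and protocol wording and a few table rows. If the Week 1 rating in the visit text stands, no new assessment is needed. There are two downsides. The rate in (b) will be lower than the planned one, by roughly 15 points in Group A in simulation with a true 1.5-grade effect at kappa 0.60, so the planned rate stays as the main figure. The estimate in (a) is imprecise: 0 of 10 has an exact upper limit of 1 − 0.025^(1/10) = 31%, and 1 of 10 has an interval of 0.3-44.5%.
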